**NCT 04016844 tDCS and Glucose Uptake in Leg Muscles**

This study utilized a single-blind, randomized, SHAM-controlled, cross-over design. Each participant attended three experimental sessions, with sessions 1 (strength testing and treadmill familiarization) and 2 (first tDCS/PET Scan session) separated by at least 3 days to allow for ample recovery after strength testing and sessions 2 and 3 (first and second tDCS/PET sessions) separated by at least 7 days to allow the tDCS effects to subside. The experimental protocol is shown in Figure 1. During Session 1, subjects were consented and then filled out the Patient Determined Disease Scale (PDDS), which is strongly correlated with and is considered an alternate assessment to the Expanded Disability Disease Status Scale (EDSS) and the fatigue severity scale (FSS) questionnaires. The subjects then completed isokinetic strength testing to objectively determine their more-affected (weaker) leg. Subsequently, the subjects walked on a treadmill to self-select a comfortable walking pace, which was utilized in experimental sessions 2 and 3. At the beginning of Session 2 and 3, blood glucose, height, and weight were measured, and an IV catheter was inserted to facilitate FDG administration. Prior to Sessions 2 and 3, the subjects fasted for a minimum of 6 h and blood glucose was required to be  $\leq 200$  mg/dL to proceed with FDG administration and the PET scanning. The subjects then sat comfortably in a chair and received 20 min of SHAM or tDCS (3 mA; stimulation condition was randomized) targeting the motor cortex corresponding to their more-affected leg, as determined in the strength testing (see below). The subjects then rested for 10 min to allow for optimal stimulation effects. After this rest period, the subjects walked on a treadmill for 20 min at the speed determined in Session 1. Two minutes into the walking,  $\sim 10 \pm 10\%$  mCi of FDG was injected via IV injection. Immediately after the 20-min walking task was completed, the subjects underwent positron emission tomography/computed tomography (PET/CT) imaging.

**Data Analysis and Statistics**

Twenty regions of interest (ROIs) were drawn on the CT scan from each session (SHAM and active) by the same investigator to locate the lower limb skeletal muscles. The muscles that comprise the knee extensors (rectus femoris, vastus medialis, vastus intermedius, and vastus lateralis) and knee flexors (semimembranosus, semitendinosus, long head of the biceps femoris, short head of the biceps femoris, gracilis, and sartorius) were identified via visual inspection in the upper leg, and the plantar flexors (gastrocnemius, soleus, peroneus longus, peroneus brevis, flexor digitorum longus, flexor hallucis longus, and tibialis posterior) and dorsiflexors (tibialis anterior, extensor digitorum longus, and extensor hallucis longus) were distinguished in the lower leg. Figure 2 displays a representative upper leg CT image with ROIs identified, a corresponding PET image, and the CT and PET images co-registered. As a result of FDG uptake occurring during the treadmill task, glucose uptake (GU) values closely reflect FDG uptake during the task. For each ROI, standardized uptake values (SUVs) were calculated based on the injected FDG dose and subjects' body weight. Despite the fasted state of the subjects, SUVs may be affected by varying insulin levels during Sessions 2 and 3. Therefore, SUV data were analyzed without normalization and as values normalized to the liver activity as a reference tissue. Moreover, SUV asymmetry indices (AIs) were calculated to determine the magnitude of asymmetry between the more- and less-affected legs with a previously used equation:  $((\text{less-affected side} - \text{more-affected side}) / ((0.5) \times (\text{less-affected side} + \text{more-affected side}))$ .

side))  $\times 100$ ). An AI value  $\geq 10\%$  was considered asymmetric. The relative distribution ((standard deviation / mean)  $\times 100$ ) of GU values in PET image voxels within each muscular ROI was calculated as an index of spatial glucose uptake heterogeneity (GUh). The data were analyzed using PMOD Version 4.001 (PMD Technologies LLC, Zurich, Switzerland).

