#### Statistical Analysis

Mean  $\pm$  standard deviation SUVs and GUh for each muscle group (i.e., knee extensors, knee flexors, plantar flexors, and dorsiflexors) were calculated for each subject, and statistical analyses were performed for each muscle group. Normality assumptions were evaluated by way of histograms, Q-Q plots, and the Shapiro–Wilk test. Because these assumptions were met, paired t-tests were performed for each participant to compare the muscle groups of each leg between conditions (e.g., left knee extensors during SHAM vs. left knee extensors during tDCS). Significance was accepted at  $p < 0.05$ , and Cohen's d effect size was calculated for all significant results. Analyses were performed using GraphPad Prism 8.1.2 (GraphPad Software, San Diego, CA, USA).

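### Raw SUV, liver-normalised SUV and GUh are each tested in four muscle groups of both legs at p < 0.05 (24 comparisons), with no deciding measure or leg and no multiplicity control

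*Combined protocol and SAP*

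**What the plan says.** The Data Analysis and Statistics section defines the outcomes. For uptake, "SUV data were analyzed without normalization and as values normalized to the liver activity as a reference tissue". The reason given is that insulin may vary between the two imaging sessions and affect SUV, even in fasted subjects. The section also defines GUh, the coefficient of variation of uptake across voxels in a muscle, and an asymmetry index (AI) between the legs.

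The Statistical Analysis section sets the tests. Both measures are summarised over four muscle groups, and testing follows the same split: "statistical analyses were performed for each muscle group". The comparison is between SHAM and tDCS within each leg: "paired t-tests were performed for each participant to compare the muscle groups of each leg between conditions". The threshold follows: "Significance was accepted at $p < 0.05$ , and Cohen's d effect size was calculated for all significant results".

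The opening design section says that stimulation was delivered "targeting the motor cortex corresponding to their more-affected leg, as determined in the strength testing". The analysis section does not come back to this. Its worked example names a left-leg muscle group, without saying whether that leg is the more-affected one.

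Nowhere do the documents call an outcome primary, rank the SUV versions, name a deciding leg or muscle group, adjust for multiple tests, or say what follows if the two SUV versions disagree.

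**The concern.** Raw and liver-normalised SUV are two measurements of the same quantity. The plan's reason for having both is that they may differ between sessions, and a rule is needed in exactly that case. None is given. The design also points to one leg, but the tests are set out for both legs without distinction.

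At stake is the meaning of a significant result. With many tests at 0.05 and none designated, no result is defined in advance as negative for tDCS, and an isolated chance finding cannot be told from the answer to the trial's question. Computing Cohen's d only for significant results draws further attention to whichever tests cross the threshold, but the point stands without it.

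**Working it through.** **No figure to reproduce.** The documents state no sample size, number of comparisons or family-wise error rate. The only number given is the per-test threshold of 0.05; two-sided testing is assumed.

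**Count.** Inputs from the two analysis sections:
- measures: raw SUV, liver-normalised SUV, GUh = 3
- muscle groups: 4
- legs: 2

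3 × 4 × 2 = 24. This assumes that each paired t-test runs across participants and that GUh is tested in the same way as SUV. The AI is left out because no between-condition test is described for it.

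**If the tests were independent.** P(at least one false positive) = 1 − (1 − 0.05)^k, with 0.05k false positives expected.

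| Tests counted | k | Chance of at least one | Expected number |
|---|---|---|---|
| All three measures | 24 | 0.708 | 1.2 |
| Both SUV versions | 16 | 0.560 | 0.8 |
| One SUV version, both legs | 8 | 0.337 | 0.4 |
| One SUV version, one leg | 4 | 0.186 | 0.2 |

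**Allowing for correlation.** The tests share subjects, so independence is an upper case. Paired t-tests were simulated with no tDCS effect anywhere (40,000 replicates). The sample sizes and correlations are all assumed. The chance of at least one p < 0.05 among the 24 was:

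| Correlation among all tests | n = 8 | n = 12 | n = 20 |
|---|---|---|---|
| 0 (checks the formula) | 0.704 | 0.711 | 0.709 |
| 0.3 | 0.622 | 0.609 | 0.608 |
| 0.5 | 0.499 | 0.490 | 0.471 |
| 0.7 | 0.357 | 0.342 | 0.329 |
| 0.9 | 0.189 | 0.177 | 0.168 |
| Structured* | 0.523 | 0.508 | 0.499 |

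*Raw with liver-normalised SUV 0.8, GUh with SUV 0.2, muscle groups 0.6, legs 0.7.

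A second simulation (n = 10, raw and liver-normalised SUV correlated 0.8, GUh independent of SUV) gave 0.59, 0.53, 0.43 and 0.37 at between-muscle correlations of 0.3, 0.5, 0.7 and 0.8, and about 0.29 at 0.9. GUh and SUV come from the same voxels, so their independence is doubtful; assuming a link lowers the 0.37 to about 0.29–0.36.

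**The two SUV versions alone.** In one muscle group of one leg, counting either version as positive raises 5% to about 8% if they correlate 0.8, to 7.4% at 0.9 and to 5.8% at 0.99 (n = 10, assumed). The choice of version therefore adds little when the two nearly coincide. Most of the inflation comes from the number of muscle groups, legs and measures.

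**The case against.** **The two SUV versions have a purpose.** They can fairly be read as a check on a named between-session confounder. This stands, and it rules out simply declaring raw SUV decisive, since the plan itself says SUV may be affected by insulin. It does not supply the missing rule for disagreement.

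**The test sentence says the t-tests were done for each participant.** Read literally, the tests would lie within one person, the pairs would be ROIs within a muscle group, and there would be 24 tests per participant. Neither the 71% nor the simulations describe that analysis. The sensible reading is across participants, but it is an assumption. The literal reading only adds tests.

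**The size is driven by assumptions.** This also stands. Neither n nor any correlation is given, and strong correlation brings the rate below 20%. In the cases examined, it stays well above 5%.

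**The study may be exploratory.** Many outcomes are acceptable in a small exploratory study, but the documents do not describe this one as such.

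**The text is in the past tense and reports that normality was met.** On its face, data had been examined. A hierarchy named afterwards would not undo any selection, which limits what the fix can achieve.

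**Conclusion.** The point holds: 24 comparisons at 0.05, with no deciding measure or leg, no multiplicity control and no rule for discordant SUV versions. The chance of at least one false positive is 71% under independence and roughly 17% to 62% for assumed common correlations of 0.9 down to 0.3 with n from 8 to 20. The count rests on reading the tests as running across participants.

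Three stronger readings are not supported:
- A reader might take 71% as the trial's error rate. It is the independence figure, and these tests are very probably positively correlated.
- A reader might infer that the plan treats any single p < 0.05 as proof of a tDCS effect, or gives the less-affected leg equal weight. The documents set a threshold for each test; they assign no weights and state no such decision rule. The defect is that the rule is absent.
- A reader might infer that an SUV version or leg was chosen after seeing the results. The documents show no such choice. They only leave room for one.

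**What to change.** 1. Make one comparison decisive: the tDCS–SHAM difference in SUV of the more-affected leg, pooled over its muscle ROIs, by a paired test across participants at 0.05. Correct the wording that suggests a separate test in each participant.
2. Choose one SUV version for that comparison and give a reason that addresses the insulin concern. Report the other as a sensitivity analysis, and state that the result is not robust if the two disagree.
3. Test the four muscle groups of that leg as secondary, with Holm adjustment (smallest p-value against 0.05/4 = 0.0125). Unadjusted, these four alone carry a rate of up to 0.186.
4. Label GUh, the AI and the less-affected leg exploratory.
5. If the data were already seen when the hierarchy is set, say that it is post hoc, report all comparisons, and present any unadjusted p < 0.05 as exploratory.

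This needs new wording and a re-run of the analysis on existing data, with no new data collection. The cost is that nominally significant secondary results can no longer be presented as the trial's finding. Keeping all 24 tests under Bonferroni would also control the error (0.05/24 = 0.0021 each), but it sets a much stricter threshold and still leaves open which SUV version decides.

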#### Statistical Analysis

Mean  $\pm$  standard deviation SUVs and GUh for each muscle group (i.e., knee extensors, knee flexors, plantar flexors, and dorsiflexors) were calculated for each subject, and statistical analyses were performed for each muscle group. Normality assumptions were evaluated by way of histograms, Q-Q plots, and the Shapiro–Wilk test. Because these assumptions were met, paired t-tests were performed for each participant to compare the muscle groups of each leg between conditions (e.g., left knee extensors during SHAM vs. left knee extensors during tDCS). Significance was accepted at  $p < 0.05$ , and Cohen's d effect size was calculated for all significant results. Analyses were performed using GraphPad Prism 8.1.2 (GraphPad Software, San Diego, CA, USA).

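### The only inferential test is stated per participant, but each participant has one SHAM and one tDCS session, so as worded it cannot estimate a tDCS effect

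*Combined protocol and SAP*

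**What the plan says.** The study is a randomized two-condition cross-over. The opening design description has "sessions 2 and 3 (first and second tDCS/PET sessions) separated by at least 7 days", with the stimulation condition randomized, so each participant contributes one SHAM scan and one tDCS scan.

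The Data Analysis and Statistics section lists the muscles outlined on each CT scan: 4 knee extensors, 6 knee flexors, 7 plantar flexors and 3 dorsiflexors. It warns that "SUVs may be affected by varying insulin levels during Sessions 2 and 3", and for that reason "SUV data were analyzed without normalization and as values normalized to the liver activity as a reference tissue".

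The Statistical Analysis section says that mean and standard deviation uptake and heterogeneity per muscle group "were calculated for each subject, and statistical analyses were performed for each muscle group". It then gives its one inferential rule: "paired t-tests were performed for each participant to compare the muscle groups of each leg between conditions", with the example "left knee extensors during SHAM vs. left knee extensors during tDCS", at a 0.05 threshold. The documents state no sample size, no test across participants, and no participant, period or sequence term.

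**The concern.** The unit that receives the condition is the session, and a participant has one session of each kind. A test run separately for each participant therefore has no replication of the condition. Whatever sub-units it uses, its p-value can say only whether that person's two sessions differed. It cannot separate tDCS from anything else that changed between the two days, and it does not address whether tDCS alters glucose uptake in general.

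The plan itself names one such change, insulin level. A shift that moves all muscles of a scan together would look like a consistent effect across muscles and could be counted as a tDCS effect. The exposure is likely greatest for unnormalised SUV. Liver normalisation may remove part of the shift but need not remove all of it. A pure change of scale cancels in the heterogeneity index, which is SD divided by mean. Groups with more muscles would have a higher error rate, so comparing results between muscle groups would also mislead.

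**Working it through.** **Step 1: degrees of freedom on the group means.** One participant, one leg and one muscle group give one SHAM mean and one tDCS mean. That is n = 1 pair and n − 1 = 0 degrees of freedom, so the standard error is undefined. This step needs no assumption.

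**Step 2: what a within-person test could use.** The documents name no sub-unit. The natural one is the individual muscle. The listed muscles add to 4 + 6 + 7 + 3 = 20, matching the stated number of regions. The number of pairs per test is then m = 4, 6, 7 and 3, with 3, 5, 6 and 2 degrees of freedom.

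**Step 3: error rate if muscles are the replicates.** Suppose tDCS has no effect and write the difference for muscle j as S + e_j, where S is a session shift shared by the m muscles. Let rho = var(S) / (var(S) + var(e)). The t statistic is then distributed as √(1 + m·rho/(1 − rho)) times a t variable on m − 1 df, so

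error = 2·P( t_{m−1} > t_{0.975, m−1} / √(1 + m·rho/(1 − rho)) ).

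The test is taken as two-sided, because the plan does not say. At rho = 0 the formula returns the plan's own 5% for every m.

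Worked case, knee flexors (m = 6), rho = 0.3: √(1 + 6 × 0.3/0.7) = 1.890; the critical value on 5 df is 2.571; 2.571/1.890 = 1.360; 2·P(t_5 > 1.360) = 23.2%.

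The documents give no value of rho, so a range is shown:

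| rho (assumed) | Dorsiflexors, m = 3 | Knee extensors, m = 4 | Knee flexors, m = 6 | Plantar flexors, m = 7 |
|---|---|---|---|---|
| 0 | 5.0% | 5.0% | 5.0% | 5.0% |
| 0.05 | 5.7% | 6.3% | 7.5% | 8.1% |
| 0.1 | 6.5% | 7.7% | 10.3% | 11.6% |
| 0.3 | 10.4% | 14.9% | 23.2% | 26.7% |
| 0.5 | 16.4% | 25.0% | 37.6% | 42.0% |
| 0.7 | 26.8% | 39.5% | 53.6% | 57.8% |

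Simulation at rho = 0.1, 0.3 and 0.5 agrees to within about 0.2 percentage points. The error reaches 10%, twice nominal, at rho = 0.28, 0.17, 0.10 and 0.08 for m = 3, 4, 6 and 7.

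**Step 4: false positives per person.** With 4 groups and 2 legs there are 8 tests per participant per outcome. The expected number of false positives is 2 × (sum of the four error rates). At rho = 0 this is 2 × 4 × 0.05 = 0.40, which is ordinary multiplicity. It rises to 0.55 at rho = 0.05, 0.72 at 0.1, 1.50 at 0.3 and 2.42 at 0.5. Only the excess over 0.40 comes from the unit of analysis.

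**Step 5: the participant as the unit.** Each participant supplies one group-mean difference, and these are tested across participants. The simulated error at rho = 0.5 is 4.8% to 5.2% with 6, 8, 12 or 20 participants. Those sample sizes are assumed, because none is stated. The shared session shift then sits in the between-participant error term, where it belongs.

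**The case against.** The strongest reply is that an ordinary paired t-test across the sample was meant, and that the wording loosely describes pairing within participant. The preceding sentence supports this: values are computed per subject and analyses are done per muscle group. With one mean per subject, a paired test exists only across subjects. On that reading the test is valid and the inflation does not arise. This cannot be ruled out, and the documents do not prove that the wrong test was run. The literal reading is not far-fetched, however. A per-subject standard deviation for a muscle group could be taken over its muscles. The left-versus-left example also fits one person better than a sample in which the more-affected leg may be on either side. Even if the across-sample test was done, the sentence misstates its unit, and a reader cannot tell what produced the p-values.

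Three further points limit the size of the concern:

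- Neither muscles as replicates nor any value of rho comes from the documents. Only the direction is established: the error is above 5% for any rho above 0.
- The model adds the same shift to every muscle. A multiplicative shift spreads the differences and inflates less. At rho = 0.5 with an assumed between-muscle coefficient of variation of 0.4, the simulated errors are about 13%, 20%, 31% and 36% for m = 3, 4, 6 and 7, still well above nominal.
- For the narrow question of whether one person's two sessions differed, a shared shift is signal, not error. The percentages apply to the hypothesis that tDCS has no effect. Against that hypothesis the confounding of condition with session stands without any percentage.

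Liver normalisation is a partial answer, but unnormalised SUVs are analysed as well.

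**Conclusion.** The concern holds, and this must be fixed. The sentence is the only description of the trial's inferential test. On the stated group means that test has 0 degrees of freedom. On units within a person it cannot distinguish tDCS from session. These conclusions rest on the documents alone.

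The error rates above are conditional on muscles being the replicates, on an additive shared shift and on an assumed rho: modest inflation at low rho, and more than double the nominal rate in every group at rho = 0.3. Confidence is moderate, because the analysis actually run may have been the valid across-participant one.

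**What to change.** State that the participant is the unit of inference. For each outcome, muscle group and leg (classified as more- or less-affected), reduce each participant and condition to one value. Compare tDCS with SHAM by a paired test across participants, and report the mean difference with its 95% confidence interval. Add a period term if the sample size allows. Show individual participants' results descriptively, without p-values.

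If the across-participant test is what was run, the cost is one corrected sentence. Otherwise the analysis text changes and the existing data are re-run; no new data or change of procedure is needed. The per-participant p-values are lost. Whether the chance of detecting an effect rises or falls cannot be judged, because the documents give no sample size.

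### The paired t-tests ignore the randomised order of tDCS and SHAM, so a session 2 to session 3 shift biases the estimate if the order split is unequal and costs power if it is equal.

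*Combined protocol and SAP*

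**What the plan says.** The opening design section states: "This study utilized a single-blind, randomized, SHAM-controlled, cross-over design". Session 1 is for "strength testing and treadmill familiarization". Sessions 2 and 3 each deliver one condition, and "stimulation condition was randomized". No allocation ratio, blocking or order split is given. Sessions 1 and 2 are "separated by at least 3 days to allow for ample recovery after strength testing", and sessions 2 and 3 are "separated by at least 7 days to allow the tDCS effects to subside".

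Data Analysis and Statistics accepts that "SUVs may be affected by varying insulin levels during Sessions 2 and 3". It therefore analyses SUVs both unnormalised and as "values normalized to the liver activity as a reference tissue".

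The Statistical Analysis section then says that "paired t-tests were performed for each participant to compare the muscle groups of each leg between conditions", with significance at p < 0.05. That is the only comparison described. No section mentions a period, order or sequence term, or a test for a difference between sessions 2 and 3.

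**The concern.** A paired t-test takes the mean of tDCS minus SHAM as the treatment effect. In a cross-over, each of those differences also contains the change from session 2 to session 3, with a sign that depends on which condition came first. The changes cancel in the mean only if the two orders have equal numbers. Even then they remain in the spread of the differences and so in the standard error.

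The documents give no size or direction for a shift, but they make one plausible. Session 2 may fall 3 days after isokinetic strength testing, while session 3 falls at least 3 + 7 = 10 days after it. The plan also expects insulin-related variation in SUVs over these two sessions.

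As planned, a reader cannot tell how much of a reported tDCS difference is a session difference. With an unequal split, part of any shift is counted as a tDCS effect or hides one. With an equal split, a real effect is harder to detect than it need be.

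**Working it through.** **Inputs.** From the documents: two conditions, two sessions, randomised order, a paired t-test, and a 0.05 level (two-sided is assumed). Sample size, order split, SD, effect size and session shift are not stated, so there is no planned figure to reproduce, and every number below is illustrative. The test is read as running across participants.

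**Notation.** D = tDCS minus SHAM for one participant; τ = true effect; δ = mean session 3 minus session 2 shift; n_S and n_T = numbers with SHAM first and tDCS first; n = n_S + n_T. The unit is the SD of D within an order group.

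**Step 1: the estimate.**
- SHAM first: E(D) = τ + δ.
- tDCS first: E(D) = τ − δ.
- Hence E(mean D) = τ + δ(n_S − n_T)/n.

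For n = 10 and δ = 0.5 the bias in absolute size is:
- 6:4: 0.5 × 2/10 = 0.1 SD
- 7:3: 0.5 × 4/10 = 0.2 SD
- 8:2: 0.5 × 6/10 = 0.3 SD

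**Step 2: the variance at an equal split.** The bias is zero, but the expected sample variance of D is 1 + δ²n/(n − 1). For n = 10 and δ = 0.5 this is 1 + 0.25 × 10/9 = 1.28. For δ = 1 it is 1 + 10/9 = 2.11.

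**Step 3: the adjusted estimate.** The mean of session 3 minus session 2 is τ + δ with SHAM first and −τ + δ with tDCS first. Half the difference between these is τ, whatever δ and the split.

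**Step 4: simulation.** Normal D, 400,000 trials per cell, n = 10. The paired t-test (n − 1 df) is set against the period-adjusted t-test (mean of the two order-group means, pooled variance, n − 2 df).

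Power at 5:5, τ = 1:

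| δ | Paired | Adjusted |
|---|---|---|
| 0 | 80% | 79% |
| 0.25 | 78% | 79% |
| 0.5 | 72% | 79% |
| 1 | 48% | 79% |

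At 6:4 with τ = 1 and δ = ±0.5, paired power is 81% or 62% depending on the sign of the bias; adjusted power is 77%.

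Type I error at δ = 0.5, with the chance of each split (either direction) under simple 1:1 randomisation:

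| Split | Chance | Paired | Adjusted |
|---|---|---|---|
| 5:5 | 25% | 3.0% | 5.0% |
| 6:4 | 41% | 3.7% | 5.0% |
| 7:3 | 23% | 6.1% | 5.0% |
| 8:2 | 11% (8:2 or worse) | 10.6% | 5.0% |

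Averaged over simple randomisation, the paired test's type I error is 5.0% at δ = 0.5 and 5.2% at δ = 1.

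**Step 5: other sample sizes.** With an equal split, δ = 0.5 and τ set for 80% paired power when there is no shift (100,000 trials per cell), paired against adjusted power is 71.1% against 77.5% (n = 8), 71.8% against 79.3% (n = 12) and 72.4% against 79.8% (n = 20).

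**The case against.** The strongest reply is that no systematic shift has been shown. Varying insulin levels describe variation, not a change in one direction, and a period term does not remove undirected variation. The gap after strength testing is there to allow recovery. Familiarisation, a fixed walking speed, fasting, the glucose limit and liver normalisation may all shrink a shift. A proportional session effect common to both legs would cancel in the asymmetry index, and a proportional effect would also cancel in the heterogeneity index.

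Small shifts also do little harm. At n = 10 and 5:5, the two tests have about equal power at δ = 0.2 (79.1% paired, 79.2% adjusted). At 6:4 and δ = 0.25, the root mean squared error is √(0.1 + 0.05²) = 0.320 unadjusted, against √(¼(1/6 + 1/4)) = 0.323 adjusted. The unadjusted figure becomes the larger only above about δ = 0.32. Averaged over simple randomisation the bias is zero. If the order was balanced by design, only the loss of power remains.

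Read literally, the plan's wording puts the test within each participant. Condition and session would then be fully confounded and no period term could be estimated. The across-participant reading is the likely intent, and the calculation rests on it.

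Most of this stands as a limit on size. It does not supply an adjustment. The 7-day gap is given for carry-over, not for a session shift. Liver normalisation leaves the unnormalised SUVs unprotected, and it cannot change the heterogeneity index, because a common divisor cancels from SD/mean. Randomisation removes bias on average, but this trial has one realised split, and at n = 10 simple randomisation gives an unequal split with probability 1 − 0.246 = 75%.

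**Conclusion.** The concern holds. The analysis of a randomised cross-over omits the period term, and nothing else in the plan does its work. The harm depends on two things the documents do not report: the realised order split and the size of any session shift. If the shift is about 0.25 SD or less and the split is near equal, little is lost. At 0.5 SD and n = 10 the paired test loses about 7 points of power at 5:5 relative to the adjusted test, carries a 0.1 SD bias at 6:4, and exceeds 5% type I error at 7:3 and beyond. These figures assume normal differences, a two-sided 5% test across participants and, for the power figures, a true effect of 1 SD. They show what could happen. They do not show that the trial's results are biased. The change should be made because it is standard for this design and lets the reader judge.

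**What to change.** For each outcome, estimate the condition effect from a model with condition and period as fixed terms and participant as random. With complete pairs this is equivalent to half the difference between the two order groups in mean session 3 minus session 2. Report the number of participants in each order, the period estimate with its confidence interval, and the unadjusted paired t-test alongside. State also that the tests run across participants.

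The cost is a change of SAP wording and a re-analysis of existing data, which needs only the record of which condition each participant had in each session. The drawback is lost power when there is no shift. At n = 10, paired power is 80.3% and adjusted power is 79.1% at 5:5, 77.6% at 6:4, 72.0% at 7:3 and 60.2% at 8:2. At n = 6 with a 3:3 split it is 50.8% paired against 46.4% adjusted. That loss is why both results should be shown.

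### The leg label for the SHAM–tDCS paired t-tests is undefined, and its only example (left vs left) does not match stimulation assigned by the more-affected leg

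*Combined protocol and SAP*

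**What the plan says.** The study description (under the title of the combined protocol and SAP) uses Session 1 "isokinetic strength testing to objectively determine their more-affected (weaker) leg". Stimulation in Sessions 2 and 3 is then applied "targeting the motor cortex corresponding to their more-affected leg, as determined in the strength testing". The leg that the intervention aims at is therefore set participant by participant, from strength and not from anatomical side.

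The Data Analysis and Statistics section keeps that classification for the asymmetry index, which serves "to determine the magnitude of asymmetry between the more- and less-affected legs".

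The Statistical Analysis section states the general rule for the SHAM–tDCS tests as "to compare the muscle groups of each leg between conditions". It gives one example in parentheses: "left knee extensors during SHAM vs. left knee extensors during tDCS". The same sentence says that "paired t-tests were performed for each participant". No sentence says whether legs enter these tests as left/right or as more-/less-affected. None gives the number of participants, or the share whose left leg is the weaker one.

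**The concern.** The natural question for this design is whether stimulating the cortex of the more-affected leg changes glucose uptake in that leg. A group test answers it only if the leg in the test is the leg that was targeted. The one label that the plan attaches to its significance test is anatomical side, which does not track targeting.

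An analyst who followed the example literally would build a left column and a right column across participants. If some participants are weaker on the left and others on the right, each column would hold targeted legs from some and non-targeted legs from the rest. The estimate would then be a blend, with weights set by how many participants happen to be weaker on each side. A null result could come from the labelling.

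If more-/less-affected labels were used, the text misdescribes the analysis. Leaving the label open also allows it to be chosen after the data have been seen.

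**Working it through.** The plan states no sample size, power, effect size or standard deviation, so it has no figure of its own to reproduce. The calculation below shows what a left/right group analysis would do and under what conditions.

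**From the documents**
- Targeting is by more-affected leg (study description).
- Each participant is measured under both SHAM and tDCS (cross-over design).
- The significance level is 0.05 (Statistical Analysis). Sidedness is not stated; two-sided is assumed.

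**Assumed, because the documents give no values**
- *n*, the number of participants: 10.
- *d*, the mean tDCS–SHAM difference in the targeted leg, in units of the SD of the paired difference: 1.
- *p*, the share of participants whose left leg is the weaker one: varied.
- *r*, the effect in the non-targeted leg divided by the effect in the targeted leg: varied.

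**Formulas for the left-leg test across participants**
- Mean difference = *d* × [*p* + (1 − *p*) × *r*]
- Variance = 1 + *p*(1 − *p*) × [*d*(1 − *r*)]²
- Standardised effect dz = mean / √variance
- Power from the noncentral t distribution with *n* − 1 degrees of freedom, checked by simulation

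**Results, *n* = 10, *d* = 1**

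| Case | Mean | Variance | dz | Power |
|---|---|---|---|---|
| Legs labelled by more-affected side | 1.00 | 1.00 | 1.00 | 80% |
| Left leg, *p* = 0.5, *r* = 0 | 0.5 × 1 + 0.5 × 0 = 0.50 | 1 + 0.25 × 1 = 1.25 | 0.45 | 22–24% |
| Left leg, *p* = 0.5, *r* = 0.5 | 0.5 + 0.5 × 0.5 = 0.75 | 1 + 0.25 × 0.25 = 1.0625 | 0.73 | about 54% |
| Left leg, *p* = 0.8, *r* = 0 | 0.8 + 0.2 × 0 = 0.80 | 1 + 0.16 × 1 = 1.16 | 0.74 | about 55% |
| Left leg, *r* = 1 (any *p*) or *p* = 1 | 1.00 | 1.00 | 1.00 | 80% |

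In the second row, 22% is for exactly five participants weaker on each side, and 24% is for weaker side varying at random with probability one half. The variance of 1.25 describes the random case.

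**Other assumed values.** With *d* = 0.8 and *n* = 15, labelling by more-affected leg gives 82% power. The left-leg test at *p* = 0.5 gives 27% (*r* = 0), 56% (*r* = 0.5) or 82% (*r* = 1). At *p* = 0.8 and *r* = 0 it gives 59%.

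**Full cancellation.** The mean is zero at *p* = 0.5 only if *r* = −1: 0.5 + 0.5 × (−1) = 0. This needs equal and opposite effects in the two legs.

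**The case against.** The strongest reply is that the left/left wording is only an example under a rule that speaks of each leg. It may show no more than that the same muscle group in the same leg is paired across conditions. That stands. A reader might infer that the endpoint is indexed to the wrong leg, but the documents do not establish a left/right analysis.

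Second, the sentence says the tests were done for each participant. Within one participant the left leg has the same targeting status in both sessions, so left vs left mixes nothing. This also stands: mixing arises only when left legs are combined across participants. The literal reading does not settle the matter, though. It yields no group estimate, and left/right results could not be interpreted without knowing which leg was targeted.

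Third, the more-/less-affected classification already appears in the study description and in the asymmetry index, so a reader could carry it into the t-tests. That is a fair reading, but the text does not state it and the only example points the other way.

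Fourth, a reader might infer that left/right labelling necessarily dilutes or cancels the effect. It does not. Dilution needs weaker sides that differ between participants and a smaller response in the non-targeted leg. Both are plausible: testing each person to find the weaker leg suggests that side was expected to vary. The documents state neither. They give no evidence of opposite effects in the two legs, so cancellation is only a limiting case.

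**Conclusion.** The point holds as an ambiguity with a possible analytic consequence. The Statistical Analysis section leaves the leg label undefined, and its only example is at odds with the targeting rule and with the labels used for the asymmetry index. It is not a demonstrated analysis error.

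The size is conditional. Under the assumed 10 participants and 1 SD effect, a left/right group test could have anything from no loss of power to a fall from 80% to about 22–24% in the cases tabulated, with intermediate cases near 54–55%. The lowest figure is one point in a wide range and should not be quoted alone. All of *n*, *d*, *p* and *r* are assumptions.

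**What to change.** State in the Statistical Analysis section that legs are classified by the Session 1 strength test. For every SUV, liver-normalised SUV and GUh comparison, specify two contrasts per muscle group, each tested across participants:

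- more-affected (targeted) leg, SHAM vs tDCS;
- less-affected leg, SHAM vs tDCS.

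Replace the left/left example with one in these terms, and reword the phrase about testing for each participant so that the unit of analysis is clear. If left/right labels were in fact used, rerun the tests under the Session 1 labels and say so.

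The label already exists, because it was needed to direct the stimulation. The number of tests does not change: four muscle groups by two legs is eight per measure under either labelling. The cost is a sentence or two of text and, at most, relabelling and reanalysis of existing data.
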